9 ASSESSMENT OF IMAGING TECHNIQUES

9.1 PRIMARY ANALYSIS

Analysis of [¹²⁴I]mIBG PET/CT and [¹²³I]mIBG planar scintigraphy will be performed retrospectively by an agreed number of observers who are experienced in the assessment of neuroblastoma. The observers will perform the analysis separately from each other and will be blinded from the scores of the other observers. An observer will perform their review of each modality for a patient several weeks apart. [¹²³I]mIBG imaging and [¹²⁴I]mIBG PET/CT imaging will be reviewed on a Hermes workstation (Hermes Medical Solutions, Sweden). Observers may perform their assessment of study imaging data in batches throughout the study but will not share their scores until the conditions are met to trigger the interim and final analyses as described in section 12.2.

For each modality, suspected lesions will be judged positive, negative, or equivocal with regard to neuroblastoma involvement by each observer. A final determination of each lesion as positive, negative or equivocal will be established through consensus between all observers:

- Positive – all reviewers consider it positive
- Negative – all reviewers consider it negative
- Equivocal – fewer than all reviewers can agree on whether the lesion is positive or negative

The scores for each modality will be submitted to the statistician at the interim and final analyses to meet the primary endpoint. The percentage of positive findings identified on routine [¹²³I]mIBG planar scintigraphy also identified by the novel [¹²⁴I]mIBG PET/CT will be determined. Recruitment will cease during the interim analysis.

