3.1.1 Total number of positive lesions recorded

The total number of lesions will be provided to the Statistician via validated listings from the Sponsor. Data will be recorded in the eCRF by the Trial Manager at the Central Imaging Unit and Source Data Verified (SDV'd) by a Sponsor Clinical Research Associate. The Sponsor Clinical Study Manager will perform a data review before the eCRF is locked and listings are provided to the Statistician.

In summary, the following data will be provided to the Statistician for each evaluable patient for each imaging modality as calculated by each individual Reviewer and as a consensus:

- Number of lesions in each skeletal segment and total number of lesions using the CURIE method (i.e. all lesions with a score of 4 or 5) and also:
 - Total number of lesions with a confidence score of 1
 - Total number of lesions with a confidence score of 2
 - Total number of lesions with a confidence score of 3
 - Total number of lesions with a confidence score of 4
 - Total number of lesions with a confidence score of 5
- Number of lesions in each skeletal segment and total number of lesions using the SIOPEN method (i.e. all lesions with a score of 4 or 5) and also:
 - Total number of lesions with a confidence score of 1
 - Total number of lesions with a confidence score of 2
 - Total number of lesions with a confidence score of 3
 - Total number of lesions with a confidence score of 4
 - Total number of lesions with a confidence score of 5

For example, one Patient's PET/CT scan will have the data above provided but as three or more sets (for detail of the number of reviewers, see the Imaging Review Manual):

- Reviewer 1's data set
- Reviewer 2's data set
- Consensus data set

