3.1.2 Confidence scores

For each lesion (or for each SIOPEN area in which diffuse disease is noted), the observer (or group of observers for the consensus opinion) will also note a confidence score to measure their certainty of the lesion being malignant, on a 5 point scale from 1 (negative) to 5 (definitively positive). See section 3.1.1 detailing how this data will be provided to the Statistician.

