4.1 General Principles

All endpoints will be summarised using descriptive statistics. Rates will be summarised using counts and percentages, continuous variables will be summarised using n, mean, standard deviation, median and quartiles. Demographics will be presented for all patients in the safety analysis sets. Total numbers of patients in each analysis set will be given with explanations for any exclusions.

Agreement between the same endpoints measured using different modalities will be reported using descriptive statistics only (summary measures of agreement with 95% confidence intervals, and cross-tabulations or line listings directly comparing two sets of measurements) unless specified below.

Additional data may be summarised by CRUK as required for reporting and will be documented separately in the Clinical Study Report.

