4.2 Analysis Methods

4.2.1 Primary endpoint

SIOPEN total numbers of lesions detected on [¹²⁴I]mIBG vs [¹²³I]mIBG will be compared as follows:

In the first stage, a total of at least 9 evaluable patients will be recruited, with a combined total of at least 50 lesions positive on [¹²⁴I]mIBG PET/CT. Initially an exact one-sided binomial test of the null hypothesis: $p \geq 97\%$ will be done using $\alpha = 0.05$. If this is rejected in favour of the alternative hypothesis $p < 97\%$, the study will be stopped early for futility.

If the null hypothesis is accepted, a further one-sided binomial test of the null hypothesis, $p \leq 90\%$ will be done using $\alpha = 0.025$. If this is rejected in favour of the alternative hypothesis $p > 90\%$ then the study may be stopped early for efficacy. If this null hypothesis is not rejected, the study will continue to the second and final stage.

Only if following the interim analysis recruitment is to continue, a second stage will be required and will end when an overall total of at least 33 evaluable patients with at least 100 lesions have been recruited. An exact one-sided binomial test of the null hypothesis, $p \leq 90\%$, will be done using $\alpha = 0.025$. If this is rejected in favour of the alternative hypothesis $p > 90\%$ then the study will be declared a success.

All above tests will be done using the following method: For each patient, the total number of lesions assessed as positive by consensus opinion (with confidence score 4 or 5) on [¹²³I]mIBG planar scintigraphy is referred to as n_{123} , and the total number of lesions assessed as positive by consensus opinion (with confidence score 4 or 5) on [¹²⁴I]mIBG PET/CT is referred to as n_{124} , with the minimum of these two numbers known as n_{\min} . The primary endpoint will be reported by the sum of n_{\min} over all patients, divided by the sum of n_{123} over all patients.

In addition, for each patient the difference and ratios between n_{123} and n_{124} will be calculated and the distribution of these variables will be summarised using the median, upper and lower quartiles. The number and percentage of patients with n_{124}/n_{123} less than 1, equal to 1 and greater than 1 will be reported.

Population to be used: Evaluable population & sensitivity population

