1. To show that [¹²⁴ I]mIBG PET/CT can detect an equal or greater number of neuroblastoma lesions compared to conventional [¹²³ I]mIBG planar scintigraphy.	1. Comparison of the percentage of lesions detected as positive by [¹²³ I]mIBG planar scintigraphy which are also considered positive with [¹²⁴ I]mIBG PET/CT.	Analysis will be done per skeletal segment as defined in table 1 below. This is because each imaging modality covers specific skeletal areas. Again, this analysis will be repeated separately for soft tissue segment.

Secondary objectives	Endpoints	Change in analysis with rationale
1. To show that [¹²⁴ I]mIBG PET/CT can detect an equal or greater number of neuroblastoma lesions compared to conventional [¹²³ I]mIBG scintigraphy with 3D imaging by SPECT (single photon emission computerised tomography).	1. Comparison of the percentage of lesions detected as positive by [¹²³ I]mIBG SPECT which are also considered positive with [¹²⁴ I]mIBG PET/CT.	Analysis will be done per skeletal segment as defined in table 1 below. This is because each imaging modality covers specific skeletal areas. Again, this analysis will be repeated separately for soft tissue segment.
2. Assessing the safety and toxicity profile of a single intravenous administration of [¹²⁴ I]mIBG.	2. Determining the causality of each adverse event to [¹²⁴ I]mIBG and grading severity according to National Cancer Institute Common Toxicity Criteria for Adverse Events (NCI CTCAE) version 4.02.	N/A

Tertiary objectives	Endpoints	Change in analysis with rationale
[REDACTED]	[REDACTED]	[REDACTED]
[REDACTED]	[REDACTED]	[REDACTED]
[REDACTED]	[REDACTED]	[REDACTED]
[REDACTED]	[REDACTED]	[REDACTED]
[REDACTED]	[REDACTED]	[REDACTED]

Tertiary objectives	Endpoints	Change in analysis with rationale

	

	

Others:

- Summary of SIOPEN & CURIE scores will be reported descriptively as mean, SD, median, IQR and ranges.

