- Sensitivity/Specificity to be calculated on positive lesions for each imaging modality, [123I]mIBG planar scintigraphy, [123I]mIBG SPECT and [124I]mIBG PET/CT versus the gold standard of the consensus results (from the combined read of [123I]mIBG planar scintigraphy, [123I]mIBG SPECT and [124I]mIBG PET/CT) for all patients and patients with < 20 lesions.

Table 1: Summary of skeletal segments per each imaging modality.

Skeletal Segments		Subject:			
Curie	SIOPEN	[¹²³ I] mIBG Planar	[¹²³ I] mIBG SPECT/CT	[¹²⁴ I] mIBG PET/CT	[REDACTED]
		Vertex to feet	Abdomen & pelvis	Vertex to feet	
Skull & facial bones	Skull & facial bones	✓	x	✓	[REDACTED]
Thorax	Thorax	✓	✓	✓	
Humeri	Humeri L	✓	x	✓	
	Humeri R	✓	x	✓	
Forearms	Forearms L	✓	x	✓	
	Forearms R	✓	x	✓	
Spine C/T (includes Sacrum)	Spine (includes Sacrum)	✓	✓	✓	
Spine L/S (includes Sacrum)		✓	✓	✓	
Pelvis	Pelvis	✓	✓	✓	
Femora	Femora L	✓	x	✓	
	Femora R	✓	x	✓	
Tibiae/fibulae	Tibiae/fibulae L	✓	x	✓	
	Tibiae/fibulae R	✓	x	✓	
Soft Tissue	Soft Tissue	✓	✓	✓	

Authorisation

Author
 
Signature:Date:
 
Name & Position: [REDACTED]

Peer Reviewer
 
Signature:Date:
 
Name & Position: [REDACTED]

Approval
 
Signature: Date:
 
Name & Position: [name] (CI)

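### SAP addendum: sensitivity and specificity are set against a combined read of the same three scans, so they show agreement with that read and not diagnostic accuracy

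*Combined protocol and SAP*

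**What the plan says.** The last item of the Others list in the SAP addendum reads "Sensitivity/Specificity to be calculated on positive lesions for each imaging modality", names planar scintigraphy, SPECT and PET/CT, and sets them "versus the gold standard of the consensus results (from the combined read of [123I]mIBG planar scintigraphy, [123I]mIBG SPECT and [124I]mIBG PET/CT". It is to be done for all patients and for patients with fewer than 20 lesions.

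Four other places bear on it.

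- **Positive and negative calls.** SAP 4.2.1 counts a lesion when it is "assessed as positive by consensus opinion (with confidence score 4 or 5". SAP 3.1.2 grades certainty "on a 5 point scale from 1 (negative) to 5 (definitively positive". Protocol 9.1 keeps an equivocal class for lesions where "fewer than all reviewers can agree on whether the lesion is positive or negative".
- **Coverage.** For the primary and first secondary objectives the addendum moves to analysis by skeletal segment, with soft tissue separate, and explains: "This is because each imaging modality covers specific skeletal areas". Table 1 lists the segments for each modality.
- **Availability of SPECT.** Protocol 9.2 reads SPECT only in patients who had it as part of routine imaging.
- **Data supplied.** For each modality, SAP 3.1.1 gives the statistician the "Number of lesions in each skeletal segment and total number of lesions using the SIOPEN method", and the same for Curie.

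**The concern.** Sensitivity and specificity are properties of a test against the truth about disease. Here the reference is built from the three tests being judged, and the visible text of the item names nothing outside them. Histology appears only as a patient-level entry criterion (Protocol 4.1.1).

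The label matters because the protocol uses these terms for the disease itself. Its summary hypothesis in section 2.6 is that PET/CT will be sensitive and specific for neuroblastoma tumour, and the same section makes later studies depend on showing enough diagnostic accuracy. A figure called sensitivity against a gold standard would be read as an answer to that question.

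Two gaps add to this. Specificity needs a count of true negatives, and the item defines none. And SPECT could be charged with missing lesions that it never imaged.

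**Working it through.** The plan states no figure for this analysis, so there is nothing to reproduce.

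**1. Index tests against reference.** Index tests: planar, SPECT, PET/CT. Components of the reference: planar, SPECT, PET/CT. The two lists are identical. A lesion visible on none of the three scans enters neither numerator nor denominator of any of the sensitivities.

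**2. Can the direction of the difference be fixed?** The visible text does not say how conflicting scans are resolved in the combined read. Assume, for illustration only, that each scan has a true sensitivity and specificity of 0.80, that the scans err independently given disease status, and that half of the candidate sites are diseased.

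- *Any positive scan makes the read positive.* P(read positive) = 0.5 × (1 − 0.2³) + 0.5 × (1 − 0.8³) = 0.5 × 0.992 + 0.5 × 0.488 = 0.740. P(PET/CT positive) = 0.5 × 0.8 + 0.5 × 0.2 = 0.500. Apparent sensitivity = 0.500/0.740 = 0.676. Apparent specificity = 1.00, because a negative read requires every scan to be negative.
- *Majority.* P(read positive) = 0.5 × 0.896 + 0.5 × 0.104 = 0.500. P(both positive) = 0.5 × 0.8 × (1 − 0.2²) + 0.5 × 0.2 × (1 − 0.8²) = 0.384 + 0.036 = 0.420. Apparent sensitivity = 0.420/0.500 = 0.84, and apparent specificity is also 0.84.
- *PET/CT decides.* Both are 1.00 by definition.

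| Rule (true value 0.80 for both) | PET/CT sensitivity, 50% / 80% of sites diseased | PET/CT specificity, 50% / 80% |
|---|---|---|
| Any positive | 0.676 / 0.763 | 1.00 / 1.00 |
| Majority | 0.84 / 0.852 | 0.84 / 0.805 |
| PET/CT decides | 1.00 / 1.00 | 1.00 / 1.00 |

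Apparent sensitivity falls on both sides of the truth. Specificity can also fall below it. With assumed true sensitivity/specificity of 0.70/0.95 (planar), 0.80/0.90 (SPECT) and 0.90/0.70 (PET/CT), and 80% of sites diseased, the majority rule gives PET/CT an apparent specificity of 0.65.

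**3. Negative units.** Scores 4 and 5 are positive and score 1 is negative. Scores 2 and 3 are not assigned to either side for this analysis, and Protocol 9.1 has a third class. The item says only that the calculation is on positive lesions, so the specificity denominator is open.

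**4. SPECT coverage, counted from Table 1.**

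- Curie rows ticked for SPECT: thorax, cervical/thoracic spine, lumbar/sacral spine, pelvis, soft tissue = 5 of 10.
- SIOPEN skeletal rows ticked: thorax, spine, pelvis = 3 of 12, plus soft tissue.

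Let f be the fraction of reference lesions that lie outside the SPECT field or in patients without SPECT. If they are counted, SPECT sensitivity ≤ 1 − f. For assumed f = 0.10, 0.20 and 0.50 the ceiling is 90%, 80% and 50%. The documents give no value for f, and the share of rows ticked does not supply one, since lesions need not be spread evenly over rows.

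**5. Units if specificity is defined per patient-segment.** On the 12 SIOPEN skeletal rows: 12 × 33 = 396 units at 33 patients and 12 × 9 = 108 at 9. For SPECT, at most 3 × 33 = 99 and 3 × 9 = 27.

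**The case against.** The strongest reply is that this is a labelling matter. The item discloses the make-up of the reference in the same sentence, the analysis is descriptive, and no visible objective is stated as sensitivity or specificity. Protocol 2.6 also words the aim as detecting mIBG-avid lesions. For that target, disease that takes up no mIBG is out of scope, and a combined mIBG read is a more natural yardstick. Table 1 sits directly beneath the item, so an analyst may well apply its coverage without being told.

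Much of this stands, and it is why importance is low. It does not remove the point. For mIBG-avid lesions, too, each scan helps to decide the reference against which it is judged. The segment restriction is written for two named objectives and not for this item, which is specified for all patients.

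Redaction also limits what can be said. SAP section 3 speaks of up to five modalities and shows three, the last column of Table 1 is blacked out, and the rule for conflicting scans may be in the Imaging Review Manual. A reader might infer that no reference free of PET/CT is planned anywhere. The documents do not support that: Protocol 1.2 describes a read of all conventional imaging with CT and MRI, and its use may be in redacted text.

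A reader might also infer a departure from SAP 4.1, which says "Agreement between the same endpoints measured using different modalities will be reported using descriptive statistics only". That sentence goes on to except whatever is specified later, and the addendum specifies this comparison separately, so there is no contradiction.

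**Conclusion.** Wrong as written, with low importance. The planned figures measure agreement with a combined read to which each scan contributes. They do not estimate diagnostic accuracy. This follows from the wording of the item and needs no assumption. So do the missing negative unit and the missing segment restriction. The SPECT ceiling of 1 − f is exact, but f is assumed. The primary test and the stopping rules are unaffected.

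A reader might infer that reported sensitivities must be too high, because unseen lesions are left out, or that PET/CT must gain over the other scans. Neither is supported. Suppose the read holds 100 lesions, PET/CT finds 97, and 5 real lesions are seen on no scan. If all 100 are real, true sensitivity is 97/105 = 92.4%. If the 3 that PET/CT missed were false positives of another scan, it is 97/102 = 95.1%, and with no unseen lesions 97/97 = 100%. Together with the range in the working, this leaves the size and sign of the difference, and its effect on the ranking of the scans, undetermined.

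**What to change.** 1. Replace sensitivity/specificity against a gold standard with positive agreement (detection rate) relative to the combined read. State that each modality contributes to that read and that lesions seen on no scan are not counted.
2. Restrict SPECT figures to the Table 1 segments ticked for SPECT and to patients who had SPECT. Show planar and PET/CT on the same subset for comparison. Reconcile the SPECT field first: Protocol 1.2 gives chest and abdomen, while the Table 1 heading gives abdomen and pelvis and the table also ticks thorax.
3. Drop specificity, or report it only as negative agreement per patient-segment. A segment is positive if it holds at least one lesion with a consensus score of 4 or 5, so scores 2 and 3 fall on the negative side, and the plan should say so. Treat soft tissue separately, as the addendum already does. The same caveat about shared components applies.

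The cost is a change of addendum wording and a modest extra tabulation. Segment counts by modality are already supplied under SAP 3.1.1, but combined-read results by segment are not visibly listed and would be needed. The downsides are less favourable wording, fewer units for SPECT, and negative agreement that is coarser than per lesion and clustered within patients.
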